TABLE OF CONTENTS

A	INTRODUCTION	2
A1	PRIMARY HYPOTHESIS.....	2
A2	PURPOSE OF THE STUDY PROTOCOL	2
B	BACKGROUND	2
B1	RATIONALE FOR THIS STUDY	2
C	STUDY OBJECTIVES.....	9
C1	PRIMARY AIM.....	9
C2	SECONDARY AIM	9
D	INVESTIGATIONAL AGENT.....	9
D1	CLINICAL DATA TO DATE	9
E	STUDY DESIGN	10
E1	OVERVIEW OR DESIGN SUMMARY	10
E2	SUBJECT SELECTION AND WITHDRAWAL.....	10
2.a	Inclusion Criteria	10
2.a	Exclusion Criteria.....	10
2.b	Subject Recruitment Plans and Consent Process	11
2.c	Randomization Method and Blinding	11
2.d	Risks and Benefits.....	12
E3	STUDY DRUG	12
3.a	Description	12
3.b	Treatment Regimen.....	12
3.c	Method for Assigning Subjects to Treatment Groups	12
3.d	Blinding of Study Drug.....	12
F	STUDY PROCEDURES	13
F1	SCREENING FOR ELIGIBILITY	13
F2	SCHEDULE OF MEASUREMENTS	13
F3	SAFETY AND ADVERSE EVENTS.....	13
F4	STUDY OUTCOME MEASUREMENTS AND ASCERTAINMENT	15
G	STATISTICAL PLAN.....	15
G1	SAMPLE SIZE DETERMINATION AND POWER.....	15
G2	ANALYSIS PLAN.....	15
H	DATA HANDLING AND RECORD KEEPING	16
H1	CONFIDENTIALITY AND SECURITY	16
H3	CASE REPORT FORMS AND SOURCE DOCUMENTS.....	17
H4	RECORDS RETENTION	17
I	STUDY MONITORING, AUDITING, AND INSPECTING.....	17
I1	STUDY MONITORING PLAN	17
J	REFERENCES	18

A Introduction

A1 Primary Hypothesis

We hypothesize the systemic infusion of lidocaine will improve pain control in patients undergoing posterior spinal fusion for adolescent idiopathic scoliosis, decreasing opiate consumption in the acute perioperative period. We further hypothesize that lidocaine infusion will attenuate the inflammatory response to injury and surgery, and that taken together decreased perioperative opiate consumption and decreased inflammation will lead to improved longer-term outcomes including decreased chronic opiate use and improved physical function.

A2 Purpose of the Study Protocol

[figure not shown]
To evaluate the efficacy of intravenous lidocaine to reduce opioid consumption, improve recovery, and reduce the systemic inflammatory response to surgery posterior spinal fusion for AIS (Adolescent Idiopathic Scoliosis).

B Background

B1 Rationale for this Study

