Figure 2. **Opioid use for chronic pain is associated with worse complaints and less improvement.** Preoperative and 1-year followup patient reported outcomes (NRS-Back, ODI) for patients undergoing complex thoracolumbar reconstructions.

Intravenous Lidocaine to Reduce Postoperative Opioid Consumption and Improve Recovery After Posterior Spinal Fusion for Adolescent Idiopathic Scoliosis

Exposure to opioids in the perioperative period may affect recovery beyond the psychological effects of dependency. Opioids are immunosuppressive, both in-vitro and in-vivo, to the innate and native immune system and can further exacerbate the immune dysfunction induced by trauma and surgery.⁶ Tissue damage, either from traumatic injury or surgery causes release of damage-associated molecular patterns (DAMPS) that serve as danger signals to the immune system, signaling the need for an inflammatory response ⁷. When the acute inflammatory response is limited to injured tissue, inflammation can contribute to hemostasis, help to prevent infection, and facilitate tissue repair ^{8,9}. In the setting of major invasive surgery, the inflammatory response can become dysregulated and extend systemically, manifest as a massive activation of the innate immune system with an almost concomitant inhibition of adaptive immunity. These pathophysiologic responses frequently complicate the care of complex-spine patients. By example, surgery for acute spinal injuries in polytrauma patients causes an increase in circulating levels of the inflammatory cytokines IL-8 and IL-6 at 7 and 24 hours after injury respectively ¹⁰⁻¹². Further, the dysregulation of immune response in these patients is frequently exacerbated by the fact that these patients often need ongoing critical care, which is itself associated with immune dysfunction ¹³.

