Peripheral nociceptors respond to injury both directly and indirectly. Outside of a normally tolerated thresholds, specialized sensory neurons response to thermal and mechanical stress to transduce a pain signal. In addition to a direct response to thermal or mechanical stimulation, nociceptors respond to neuroactive signalling molecules and inflammatory mediators produced by non-neuronal cells such as glia and leukocyte. These signals can both amplify (pro-nociceptive) or attenuate (anti-nociceptive) the response of sensory neurons.²⁹ Pro-nociceptive mediators include the canonical inflammatory cytokines TNF-alpha³⁰, IL-6³¹ and IL-1-beta³², produced in response to inflammation by innate immune cells such as monocytes and macrophages. Nociceptors express cell surface receptors that can respond directly to these mediators, decreasing the threshold for activation resulting in a pro-nociceptive effect.³³ Conversely, antiinflammatory mediators such as IL-10 can decrease sensory neuron activation, having an anti-nociceptive effect.²⁹ The effect of these mediators can be to both increase the intensity of an otherwise low-amplitude pain signal or to decrease the threshold for a response. In addition, there are cohorts of neurons that are normally that are insensitive to mechanical or heat stimulation, but in response to inflammatory mediators these neurons become sensitized to noxious mechanical or thermal stimulation, and are thereby recruited as nociceptors.^{6,34} Thus inflammation both facilitates the activation of the normal complement of peripheral nociceptors, but also recruits novel nociceptors, further amplifying the pain signal.

[figure not shown]
In patients undergoing major spine surgery, the dynamics of inflammation and pain are particularly complex. Major surgery can cause dysregulated immune response resulting in a systemic inflammatory response, characterized in part by elevated levels of circulating inflammatory mediators.³⁵ These circulating inflammatory mediators can interact with pain neural pathways across the anatomic spectrum from the peripheral nociceptors to ascending spinal tracts, broadly decreasing the threshold for activation of pain pathways, resulting in the syndrome of hyperalgesia whereby normally innocuous stimuli cause a pain response. In the setting of recovery from major spine surgery, hyperalgesia may exaggerate the pain response from minor injuries, exacerbating the challenge of pain control.

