which would correlate with decreased free-radical production with an associated decreased injury to the pulmonary vasculature. Similar results were reported by Takao et al, who reported that lidocaine infusion was associated attenuated the levels of the inflammatory cytokines TNF-alpha and IL-1beta in the BAL of rabbits with a hyperoxic lung injury¹⁶. Critically, study of PMN isolated from septic human patients demonstrate that lidocaine treatment can reduce PMN recruitment. These authors also demonstrate that lidocaine can interact directly with PMN, modulating integrin-mediated activation of protein-kinase C (PKC)-theta.¹⁵ These data support those from Hollmann et al which demonstrate that lidocaine can attenuate PMN superoxide production, which is mediated in part by outside-in integrin signalling.⁴⁰ Lidocaine modulates the systemic inflammatory response. Pretreatment with systemic lidocaine prior to endotoxin-induced acute lung injury (ALI) in rabbits resulted in decreased levels of inflammatory cytokines TNF-alpha and IL-1-beta in the bronchoalveolar lavage fluid.³⁹ Similar results were reported for both hyperoxic and hydrochloric acid induced ALI.^{16,39} Similarly, systemic infusion of lidocaine was found to ameliorate shock in a rabbit model of endotoxemia, and this was associated with a significant decrease in the circulating levels of TNF-alpha, IL-6 and IL-8.⁴¹ Analogous results were seen in both rodent and equine models of endotoxemia.⁴¹⁻⁴⁴

To demonstrate the effect of lidocaine on the immuno-inflammatory response, we measured cytokine production by human peripheral blood mononuclear cells in response to either LPS or T-cell receptor ligation with anti-CD3/anti-CD28 antibody in the presence of increasing doses of lidocaine (Figure 5). We found that lidocaine strongly inhibits cytokine production in response to both stimuli, demonstrating that lidocaine can attenuate both the innate and adaptive immune response at physiologically relevant doses. These preliminary data directly demonstrate the immunomodulatory effects of lidocaine on human leukocytes.

C Study Objectives

C1 Primary Aims

Specific Aim 1:

- a. To determine the effect of systemic lidocaine on postoperative opioid consumption following posterior spinal fusion surgery for AIS.

Specific Aim 2: Determine the effect of lidocaine infusion on the immuno-inflammatory response following posterior spinal fusion for AIS.

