Both the leukocyte frequencies and leukocyte cell surface phenotype will be measured by flow cytometry. This approach will allow hypothesis-based assessment of pathways demonstrated to contribute to the postoperative immune phenotype, while also providing data for a discovery-driven analysis to define novel mechanisms. Patients will be identified based on inclusion/exclusion criteria as described above. Blood samples with following time points: immediately preoperatively, 4 hours and 8 hours post incision, day 1 post surgery, and day 2-3 post surgery. All blood samples will be collected into 6 ml EDTA-containing vacutainers and three aliquots prepared for fixation by mixing 1.25 ml blood with 1.75 ml Proteomic Stabilizer (Smart Tube, Inc, San Carlos, CA). Following fixation, samples will be stored at -80 °C until flow cytometric analysis. For each patient and time point, one aliquot of the fixed and frozen blood will be used for immunophenotyping. The remaining aliquots will be used for mass cytometry as described and preserved as a "biobank" for potential future studies.

We will analyze signaling events in all major leukocyte subsets and compare phospho-signal median intensities between the different time points and treatment groups to define any immune modulatory effects of lidocaine during surgery.

The primary outcome measure is total, in-hospital opioid consumption following surgery for AIS. Opioid consumption will be measured in morphine-equivalent dosage (MED), to allow for the use of different opioid medications (e.g. fentanyl, hydromorphone, oxycodone) over the course of care.

Secondary outcome measures to assess recovery are the Patient Reported Outcomes Measurement Information System (PROMIS) Mobility (M) and Pain Interference (PI) domains. PROMIS is a general measure of health administered over particular health domains. The SRS-22 will be used in assessing the quality of life in AIS patients. The SRS-22r includes 22 items distributed among five different factors (pain, self-

Intravenous Lidocaine to Reduce Postoperative Opioid Consumption and Improve Recovery After Posterior Spinal Fusion for Adolescent Idiopathic Scoliosis

image/appearance, function/activity, mental health, and satisfaction with management). Each component includes five items, except for the “satisfaction with management”, which only contains two items. Secondary measures to assess the anti-inflammatory effect of lidocaine will be serum levels of IL-10, IL-4 and IL-12.

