The anticipated outcome is decreased in-hospital opioid consumption for those patients treated with intravenous lidocaine. Other anticipated outcomes are improved recovery as measured by PROMIS-M and PROMIS-PI measures at 6 weeks, 3 months, 6 months, and 12 months after surgery. We anticipate that the anti-inflammatory effect of lidocaine will reflect a smaller postoperative inflammatory response as measured by IL-10, IL-4, and IL-12.

F3 Safety and Adverse Events

Serum lidocaine levels will be drawn at 12 hours after incision and reviewed by an individual independent from the study team. Lidocaine toxicity will result in immediate cessation of study drug, unblinding, and reporting to the Medical Monitor and IRB. If intraoperative surgical, medical, or anesthetic complications occur, including cardiac arrhythmia, the study medication will be stopped and the patient withdrawn from the study. The patient will be analyzed in an intent-to-treat analysis, though they will be excluded from as-treated analyses. After surgery, patients will be seen and examined twice daily with attention to postoperative complications. As the study-drug will have completed infusion, all complications will be recorded though patients will remain enrolled in the study and analyzed per-protocol. All adverse events will be recorded up to 12 weeks after surgery. These will be captured via interview at the visit or via telephone if a clinic visit is not possible. Readmission for any reason will be recorded and details of this hospitalization will be recorded. Any reason reasonably related to the research protocol will be reported to the Medical Monitor and the IRB.

We believe there are minimal risks associated with participation in this clinical trial and with the study intervention (intravenous lidocaine). The most concerning serious adverse event that might be attributed to systemic lidocaine administration is cardiac arrhythmia/arrest. Therapeutic serum concentrations are far lower than toxic levels and we believe the risk of serious adverse events to be low. The intervention will not add time to the surgical intervention and, thus, does not pose additional risk from this perspective. All patients will receive standard of care treatment before, during, and after surgery and the study intervention will pose no risk to this.

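### The named cytokine outcomes (IL-10, IL-4, IL-12) include none of the four cytokines on which the readable rationale rests, so Aim 2b does not test the circulating-cytokine pathway the protocol describes

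*Combined protocol and SAP*

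**What the plan says.** A1 hypothesises that "lidocaine infusion will attenuate the inflammatory response to injury and surgery" and that this, together with lower opioid use, will improve longer-term outcomes. C1 lists the immune question as Specific Aim 2, in three parts: leukocyte frequencies and phenotype by flow cytometry (2a), systemic cytokines with and without lidocaine (2b), and functional changes by mass cytometry (2c). The wording of Aim 2b names no cytokine.

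The analytes are named in F2 and F4, in the same words: "Secondary measures to assess the anti-inflammatory effect of lidocaine will be serum levels of IL-10, IL-4 and IL-12". Both sections then state the expected result, that the effect of lidocaine "will reflect a smaller postoperative inflammatory response as measured by IL-10, IL-4, and IL-12".

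The argument for measuring cytokines is in B1. On surgery, it says that "surgery for acute spinal injuries in polytrauma patients causes an increase in circulating levels of the inflammatory cytokines IL-8 and IL-6". On pain, it says "Pro-nociceptive mediators include the canonical inflammatory cytokines TNF-alpha" and goes on to list IL-6 and IL-1-beta. On lidocaine, it cites a rabbit endotoxaemia model showing "a significant decrease in the circulating levels of TNF-alpha, IL-6 and IL-8", and rabbit lung-injury models showing lower TNF-alpha and IL-1-beta in lavage fluid.

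**The concern.** The cytokines that carry the argument and the cytokines that are measured do not overlap. B1 proposes that surgery puts inflammatory mediators into the circulation, that these lower the threshold for pain, and that lidocaine reduces them. A cytokine outcome can inform that chain only if it measures a mediator that the chain names.

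At stake is what may be concluded from Aim 2b, which sits under the heading of primary aims in C1. If the three measured cytokines do not differ between arms, lidocaine may still have lowered IL-6 or IL-8, and nobody would know. If they do differ, the result does not show that the described pathway was affected. Unless specimens suitable for a wider assay are kept, the omission cannot be repaired after the trial.

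**Working it through.** There is no figure to reproduce. The check sets the cytokines named in B1, by the role given to each, against the panel in F2 and F4.

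| Role in B1 | Cytokines named | Also in the panel {IL-10, IL-4, IL-12} |
|---|---|---|
| Raised by surgery (polytrauma spine surgery) | IL-8, IL-6 | none |
| Pro-nociceptive | TNF-alpha, IL-6, IL-1-beta | none |
| Lowered by lidocaine, in the circulation (rabbit) | TNF-alpha, IL-6, IL-8 | none |
| Lowered by lidocaine, in lavage fluid (rabbit) | TNF-alpha, IL-1-beta | none |
| Anti-inflammatory and anti-nociceptive | IL-10 | IL-10 |

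The first four rows together give four distinct cytokines: IL-6, IL-8, TNF-alpha and IL-1-beta. The panel contains 0 of the 4.

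In the other direction, 1 of the 3 panel members (IL-10) has a stated role, and it is the opposite of the pro-inflammatory role. The other 2 of 3 (IL-4 and IL-12) do not occur in the readable rationale. The one place where they might is Figure 5, on human blood cells exposed to lidocaine. The figure is not available and its accompanying text does not say which cytokines were measured.

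**Draw times.** F2 plans samples immediately before surgery, at 4 h and 8 h after incision, on day 1, and on day 2-3. B1 says that surgery in polytrauma patients "causes an increase in circulating levels of the inflammatory cytokines IL-8 and IL-6 at 7 and 24 hours after injury respectively", which puts IL-8 at 7 h and IL-6 at 24 h. The nearest planned draws are 8 h for IL-8 and day 1 for IL-6. The match is only approximate: B1 counts from injury in trauma patients, whereas F2 counts from incision or surgery in elective patients.

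**Specimen.** F2 collects blood into 6 ml EDTA tubes and fixes three aliquots of 1.25 ml, so 3 × 1.25 = 3.75 ml is taken for cytometry and the biobank and 6 − 3.75 = 2.25 ml is left over. The cytokine outcomes are described as serum levels, but no serum tube or cytokine assay is described. This gap exists for the present panel as much as for a wider one.

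**The case against.** The strongest case on the other side has five parts.

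- **The hypothesis is general and has other tests.** A reader might infer that the trial cannot test its inflammation hypothesis at all. The documents do not support that. A1 names no cytokine, and Aims 2a and 2c test immune modulation through cell frequencies, surface markers and intracellular signalling, with signalling compared between treatment groups. This stands, and it limits the point to Aim 2b. Cytometry does not measure circulating cytokines, so it does not repair 2b.
- **Aim 2b still gives an answer.** Three cytokines compared by arm answer a narrow question, and the aim's own wording sets no limit on analytes. This also stands. What the comparison does not address is the pathway in B1, and F2 and F4 tie the stated conclusion to the three analytes.
- **IL-10 belongs to the pain pathway.** True, but as its damping side. A lower IL-10 is not evidence of fewer pro-nociceptive mediators.
- **Figure 5 may show IL-4 or IL-12 falling with lidocaine.** It may, so one cannot say that the protocol has no lidocaine data on them. Inhibition in cultured cells would still not show that they rise after surgery or relate to pain, nor explain the absence of the other four.
- **The evidence for the four is indirect.** The surgical evidence comes from polytrauma and the lidocaine evidence from rabbits, with IL-1-beta reported only in lavage fluid. This is fair. It is nevertheless the evidence the protocol chose to argue from, and the readable text offers none for IL-4 or IL-12.

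**Conclusion.** The point holds for the cytokine component of Aim 2. The panel measures 0 of the 4 cytokines that the readable rationale names as raised by surgery, pro-nociceptive or lowered by lidocaine in animals, and 2 of its 3 members have no role in the readable text. A finding of "a smaller postoperative inflammatory response as measured by IL-10, IL-4, and IL-12" would therefore neither support nor refute the circulating-cytokine pathway in B1.

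The conclusion rests on two conditions: that F2 and F4 give the full list of cytokine outcomes, and that the missing Figure 5 holds no justification for the panel that the text leaves out. It does not extend to Aim 2 as a whole or to the general hypothesis in A1. The primary opioid outcome and the sample size in G1 are unaffected. This is a cheap improvement, not a flaw that threatens the trial.

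**What to change.** In F2 and F4:

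1. Add IL-6 and IL-8 as the lead cytokines for Aim 2b, with TNF-alpha and IL-1-beta as supporting markers. Assay them together with the three already named, at the existing draw times.
2. Analyse each as change from the preoperative sample, compared by arm. G2 sets out no cytokine analysis at present, so this needs a sentence there too.
3. Keep IL-10, IL-4 and IL-12 as exploratory, and base any statement about a smaller inflammatory response on IL-6 and IL-8.
4. If a single lead time per cytokine is wanted, pair IL-8 with the 8 h draw and IL-6 with day 1, and say that the pairing is approximate because the source times run from injury in polytrauma patients.
5. State which specimen the cytokines are measured in. Any panel needs this.

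The cost is a modest increase in assay expense and four more analytes to report (3 + 4 = 7). No new draw time is required. Naming two lead cytokines in advance keeps the longer list from turning into a search for whichever one differs.

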- a. Determine changes in leukocyte frequencies and phenotype during and following surgery by flow cytometric immunophenotyping.
- b. Assess systemic cytokine responses during and following surgery with and without IV lidocaine treatment.
- c. Define surgery- and lidocaine-induced functional changes in immune cell populations by mass cytometry.

C2 Secondary Aims

To determine the effectiveness of systemic lidocaine to improve recovery after posterior spinal fusion for AIS. We hypothesize that patients receiving intravenous lidocaine will experience faster recovery from surgery. To test this hypothesis PROMIS-Computer Adaptive Tests (CAT) for Mobility (M) and Pain Interference (PI) will be compared between groups at enrollment, 6 weeks, 3 months, 6 months, and 12 months after surgery. The Scoliosis Research Society 22 (SRS-22) will also be completed at these time points.

D Investigational Agent

D1 Clinical Data to Date

Lidocaine hydrochloride (2-Diethylamino-2', 6'-acetoxylidide monohydrochloride) is an amide-type, short-acting local anesthetic and delivered as an aqueous solution for intravenous administration. It has a half-life of 1.5-2 hours. A traditional method of administration is via epidural delivery. Epidural lidocaine is effective and this effect is due, in part, to systemic absorption. Systemic (intravenous) administration of lidocaine is a Food and Drug Administration approved method of delivery. Low plasma levels are needed for effective use, 0.5 μ g/mL to 5.0 μ g/mL. Given this low concentration required and the short half-life, continuous infusion of lidocaine is thought to be generally safe with low risk of complication.

The low plasma levels have not been associated with hemodynamic instability nor have they been associated with changes in cardiac contractility. No interactions with the autonomic nervous system have been reported and there are no known effects on sinoatrial conduction. Lidocaine is metabolized by the liver, with less than 10% excreted in urine. Complications are rare. Despite concerns for arrhythmias, intravenous lidocaine has been used in cardiothoracic

Intravenous Lidocaine to Reduce Postoperative Opioid Consumption and Improve Recovery After Posterior Spinal Fusion for Adolescent Idiopathic Scoliosis

surgery without increased rates of cardiac complications. Give this volume of evidence, we feel that intravenous lidocaine in the setting of AIS surgery is safe.

D2 Dose Rationale and Risk/Benefits

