Patients consenting to randomization will be randomized 1:1 to the control or study group. A permuted randomized block approach¹ with blocks of size 4, 6 and 8. Given the relatively large number of patients to be enrolled, no stratification will be performed. After 30 patients are enrolled, an interim analysis, without unblinding, of baseline covariates will be performed to ensure equal distribution between groups. If distribution is uneven for covariates concerning for confounding, then stratification by these covariates will be employed to ensure equal distribution with randomization.

Patient loss to follow-up can affect the randomization balance and quality. Aims 1a and 2 are in-hospital studies and outcome data will be collected during the hospital stay. Loss-to-followup is not expected during the hospital stay. Aims 1b and 3 may be affected by loss-to-followup. All efforts will be made to collect follow-up data. A scheduled spine clinic visit is the preferred method of data collection. If the patient will not attend clinic, then they will be contacted by mail, email, and/or phone. Surveys may be sent electronically for completion. At enrollment, the contact information for two family members not living with the patient will be obtained. These people will be contacted should contact with the patient be lost. Registered mail will be sent to the last known address, with a self-addressed, stamped return envelope to collect outcomes data. Administration of PROMIS-CAT and SRS are valid by telephone and email.⁴⁷

Intravenous Lidocaine to Reduce Postoperative Opioid Consumption and Improve Recovery After Posterior Spinal Fusion for Adolescent Idiopathic Scoliosis

2.d Risks and Benefits

E3 Study Drug

3.a Description

Lidocaine hydrochloride (2-Diethylamino-2', 6'-acetoxylidide monohydrochloride) is an amide-type, short-acting local anesthetic and delivered as an aqueous solution for intravenous administration. It has a half-life of 1.5-2 hours. A traditional method of administration is via epidural delivery. Epidural lidocaine is effective and this effect is due, in part, to systemic absorption. Systemic (intravenous) administration of lidocaine is a Food and Drug Administration approved method of delivery. Low plasma levels are needed for effective use, 0.5 μ g/mL to 5.0 μ g/mL. Given this low concentration required and the short half-life, continuous infusion of lidocaine is thought to be generally safe with low risk of complication.

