Safety measures to minimize/eliminate risks to human subjects and study personnel include the use of the Medical Monitor and immediate reporting of any adverse (expected or unexpected) to the project PI and project manager. If any intraoperative complications occur, such as but not limited to cardiac arrest or seizure, the study medication will not be administered and the patient will be excluded from the study. However, if one of these problems occurs after the application of the study medication the patient will be unblinded. The patient will be followed for the occurrence of further adverse events or complications.

For any serious adverse event, the Medical Monitor at the enrollment site will perform a root cause analysis and will notify the project PI in the study medication is believed to be a potential cause of the adverse event. The Monitor may recommend stopping the study. Any serious adverse event will be reported to the PI and the IRB within 10 working days.

F4 Study Outcome Measurements and Ascertainment

The primary outcome measure is total, in-hospital opioid consumption following surgery for thoracolumbar trauma. Opioid consumption will be measured in morphine-equivalent dosage (MED), to allow for the use of different opioid medications (e.g. fentanyl, hydromorphone, oxycodone) over the course of care.

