After the first 15 patients are enrolled, a group consisting of the Principal Investigator and an unengaged physician will review the AE/SAE data. The data will be reviewed blinded. If intraoperative surgical, medical, or anesthetic complications occur, including cardiac arrhythmia, the study medication will be stopped and the patient withdrawn from the study. The patient will be analyzed in an intent-to-treat analysis, though they will be excluded from as-treated analyses. After surgery, patients will be seen and examined twice daily with attention to postoperative complications. As the study-drug will have completed infusion, all complications will be recorded though patients will remain enrolled in the study and analyzed per-protocol.

Special attention will be given if adverse events occur in a higher frequency than expected given patient age and health condition. Serious adverse events, or those that are life threatening, result in death, prolonged hospitalization, readmission, cause persistent disability or require urgent intervention to prevent permanent morbidity will be monitored for up to 30 days after the drug is administered. If there appears to be an imbalance in AE/SAE, unblinding and analysis will ensue to determine if the study should continue. Early termination will occur if SAEs are linked to the treatment arm.

After 10 patients have completed the hospital phase of the study, flow and mass cytometry will be performed to ensure we are capturing cell types and signaling proteins as anticipated.

All protocol violations and SAE's will be reported to HRPO within the WU HRPO policies and procedures reporting guidelines
SAEs will be tracked through resolution.

J References

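### The only planned lidocaine level, fixed at 12 hours after incision, says little about exposure at an intraoperative event that stops study drug, and may not be drawn at all

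*Combined protocol and SAP*

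**What the plan says.** Section F3 (Safety and Adverse Events) sets the measurement: "Serum lidocaine levels will be drawn at 12 hours after incision and reviewed by an individual independent from the study team". No other section schedules a lidocaine assay. The blood draws in F2 (before surgery, 4 and 8 hours after incision, day 1, day 2-3) are described for flow and mass cytometry.

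F3 also says what follows from toxicity: "Lidocaine toxicity will result in immediate cessation of study drug, unblinding, and reporting to the Medical Monitor and IRB". It gives no toxic threshold. For intraoperative complications, "including cardiac arrhythmia, the study medication will be stopped and the patient withdrawn from the study"; I1 repeats this rule.

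For any serious adverse event, F3 says that "the Medical Monitor at the enrollment site will perform a root cause analysis". If the event follows administration of study drug, F3 unblinds the patient and continues follow-up for further events. I1 adds: "Early termination will occur if SAEs are linked to the treatment arm".

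On pharmacokinetics, D1 and E3 (3.a) say of lidocaine: "It has a half-life of 1.5-2 hours". They also say "Low plasma levels are needed for effective use", with a range of 0.5 to 5.0 µg/mL.

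**The concern.** The sample is tied to a clock time counted from incision, not to the patient's exposure. In the planned course this does no harm, because the infusion is still running at 12 hours. F3 names arrhythmia or arrest as the most concerning event that lidocaine might cause, and that same event triggers the stop. The drug then washes out for hours before the scheduled draw. Withdrawal from the study also leaves open whether the draw happens.

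At stake is the quality of the evidence for judging such an event. After an early stop, a high and an ordinary concentration at the event could both give a low 12-hour reading. In a trial of 50 patients, the attribution of a single serious event could weigh heavily on whether the trial continues.

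**Working it through.** The documents state no residual level, so there is no plan figure to reproduce. The check uses the plan's own half-life with one-phase elimination, which is an assumption.

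**Inputs**
- Draw time: 12 h after incision (F3).
- Half-life h: 1.5 to 2 h (D1, E3 3.a).
- Reference range: 0.5 to 5.0 µg/mL (D1, E3 3.a).
- Stop time s, in hours after incision: not in the documents, nor is the duration of surgery. Assumed 2 to 5 h, with 0 to 8 h as a sensitivity range.

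**Uninterrupted infusion.** The infusion starts before incision, so by the draw it has run at least 12/2 = 6 to 12/1.5 = 8 half-lives. The fraction of steady state is 1 − 2^−6 = 98.4% to 1 − 2^−8 = 99.6%. The 12-hour level is informative for these patients.

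**Interrupted infusion.** Half-lives elapsed n = (12 − s)/h; fraction remaining = 2^−n; reading from 5.0 µg/mL = 5.0 × 2^−n. In each cell the first figure is for h = 2 h and the second for h = 1.5 h.

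| Stop (h) | Half-lives | Remaining | Reading from 5.0 µg/mL |
|---|---|---|---|
| 0 | 6.0; 8.0 | 1.6%; 0.4% | 0.08; 0.02 |
| 2 | 5.0; 6.7 | 3.1%; 1.0% | 0.16; 0.05 |
| 4 | 4.0; 5.3 | 6.3%; 2.5% | 0.31; 0.12 |
| 5 | 3.5; 4.7 | 8.8%; 3.9% | 0.44; 0.20 |
| 6 | 3.0; 4.0 | 12.5%; 6.3% | 0.63; 0.31 |
| 8 | 2.0; 2.7 | 25%; 16% | 1.25; 0.79 |

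For stops at 2 to 5 h, a level at the top of the protocol's range falls below the bottom of that range by the time of the draw. From 6 h on this no longer holds throughout.

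**The reverse question.** To read 0.5 µg/mL at 12 h, the level at stopping must be 0.5 × 2^n. For a stop at 4 h this is 0.5 × 2^4 = 8 to 0.5 × 2^5.33 = 20 µg/mL.

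**Back-extrapolation.** With a known stop time, the half-life range alone makes the back-calculated level uncertain by a factor of 2^((12 − s)(1/1.5 − 1/2)) = 2^((12 − s)/6). This is 2^(7/6) = 2.2 for a stop at 5 h and 2^(10/6) = 3.2 for a stop at 2 h.

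**Two textual points that decide whether the sample is taken and what it means**
- F3 and I1 withdraw the patient from the study. F3 elsewhere keeps following a patient whose event came after study drug. Neither says whether the 12-hour sample survives withdrawal.
- F3 and I1 describe study drug as already finished once surgery is over. D2, E1, E3 (3.b) and F2 continue it until 24 hours in the PACU or PICU. If it did end with surgery, the 12-hour level would be post-infusion for every patient whose operation ended less than 12 hours after incision.

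**The case against.** The strongest defence is that the 12-hour draw is routine exposure monitoring and does that job for patients on continuous infusion. An unscheduled clinical level during an emergency is not forbidden. At most about 25 patients receive lidocaine, and only those stopped early are affected. The background section says that 2 mg/kg plus 2 mg/kg/hr stays below toxic levels, which is twice this trial's 1 mg/kg plus 1 mg/kg/hr. All of this stands, and it limits the weight of the point. It does not supply a planned measurement near the event, and an unplanned draw may not happen.

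Three stronger readings are tempting and are not supported.
- A reader might infer that the level cannot show the cause. That goes too far. Readings rise in proportion to the level at the event, a late stop leaves a measurable share (16% to 25% at 8 h, given an adequate assay), and the administered volume is recorded (D2), so back-extrapolation is possible in principle.
- A reader might infer that causality and early termination would rest on this value. Neither F3 nor I1 says so. The root cause analysis is not limited to any one kind of evidence, the patient is unblinded, and the termination rule mentions no serum level. The arm, however, shows assignment, not concentration. That a low value would be taken to clear lidocaine is conjecture.
- A reader might take a particular number of half-lives as a property of the plan. It depends on a stop time that the documents do not give.

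**Conclusion.** The point holds as an inexpensive improvement to a stated sampling rule. It does not invalidate the safety plan. For a patient stopped intraoperatively 2 to 5 hours after incision, 3.5 to 6.7 half-lives pass and about 1% to 9% of the level remains at the draw. Across stops at 0 to 6 hours the figures are 3 to 8 half-lives and 0.4% to 12.5%. Such a value is largely uninformative about exposure at the event, and withdrawal may mean there is no value at all.

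The result rests on one-phase elimination, on the protocol's half-life applying to these patients, and on the assumed stop times. It does not extend to patients on uninterrupted infusion, provided the infusion does run as D2, E1, E3 and F2 describe.

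**What to change.** This changes measurement timing only. No dose, treatment or stopping rule is proposed.

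- In F3, tie the planned sample to exposure: 12 hours after incision while study drug is running or, if study drug is stopped earlier, as close as feasible to the time of stopping, in place of the 12-hour draw.
- Record the draw time and the infusion stop time.
- Send the result to the independent reviewer and to the Medical Monitor.
- Reconcile withdrawal from the study (F3, I1) with continued follow-up after an event on drug (F3), so that it is clear this safety sample is still taken.
- Reconcile the statements that the infusion is over after surgery (F3, I1) with those that continue it to 24 hours in the PACU or PICU (D2, E1, E3 3.b, F2). This decides whether the 12-hour level is taken during infusion.

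The sampling change takes about a sentence in F3, and the reconciliations need matching edits in I1 and possibly the dosing sections. One sample is moved for a few patients and none is added. A draw during a complication may sometimes be missed. The change does not cover an event after hour 12 in a patient still on drug, whose only level would be the earlier one.
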